8.3.2 Definition of Serious Adverse Events (SAE)

A serious adverse event (SAE) as determined by the investigator is any event that results in any of the following outcomes:

1. Death
2. Life-threatening AE (“life-threatening” means that the study participant was, in the opinion of the investigator or sponsor, at immediate risk of death from the reaction as it occurred and required immediate intervention)
3. Persistent or significant incapacity or substantial disruption of the ability to conduct normal life functions
4. Inpatient hospitalization or prolongation of existing hospitalization
5. Important medical event that may not result in one of the above outcomes, but may jeopardize the health of the study participant or require medical or surgical intervention to prevent one of the outcomes listed in the above definition of serious event

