8.3.3.2 Relationship to Study Intervention

All adverse events (AEs) must have their relationship to study intervention assessed by the clinician who examines and evaluates the participant based on temporal relationship and his/her clinical judgment. The degree of certainty about causality will be graded using the categories below. In a clinical trial, the study product must always be suspect.

- **Related** – The AE is known to occur with the study intervention, there is a reasonable possibility that the study intervention caused the AE, or there is a temporal relationship between the study intervention and event. Reasonable possibility means that there is evidence to suggest a causal relationship between the study intervention and the AE.

- **Not Related** – There is not a reasonable possibility that the administration of the study intervention caused the event, there is no temporal relationship between the study intervention and event onset, or an alternate etiology has been established.

The investigator will use the following question when assessing causality of an adverse event to study drug, where an affirmative answer designates the event as a suspected adverse reaction: Is there a reasonable possibility that the drug caused the event? “Reasonable possibility” means that there is evidence to suggest a causal relationship between the drug and the adverse event.

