8.3.3.3 Expectedness

The investigator will be responsible for determining whether an adverse event (AE) is expected or unexpected. An AE will be considered unexpected if the nature, severity, or frequency of the event is not consistent with the risk information previously described for the study intervention.

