8.3.6 Serious Adverse Event Reporting

The study clinician will immediately report to the investigator any serious adverse event, whether or not considered study intervention related, including those listed in the protocol or investigator brochure and must include an assessment of whether there is a reasonable possibility that the study intervention caused the event. Study endpoints that are serious adverse events (e.g., all-cause mortality) must be reported in accordance with the protocol unless there is evidence suggesting a causal relationship between the study intervention and the event (e.g., death from anaphylaxis).

All serious adverse events (SAEs) will be followed until satisfactory resolution or until the investigator deems the event to be chronic or the participant is stable.

The investigator will be responsible for notifying the Food and Drug Administration (FDA) of any unexpected fatal or life-threatening suspected adverse reaction as soon as possible, but in no case later than 7 calendar days after the sponsor's initial receipt of the information. In addition, the sponsor must notify FDA and all participating investigators in an Investigational New Drug (IND) safety report of potential serious risks, from clinical trials or any other source, as soon as possible, but in no case later than 15 calendar days after the sponsor determines that the information qualifies for reporting.

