9.4.4 Safety Analyses

We will collect information on adverse events (AEs) during and after study drug administration. Seizures will be AE of special interest and defined by the receipt of > 1 AED. We will summarize AEs by organ system and report descriptive statistics of laboratory values. We will correlate caffeine exposure with seizure activity and NEC following the first dose of caffeine.

Following the follow-up period in the final cohort 1 participant, there will be an interim safety analysis performed by an independent safety monitor (ISM) with training in neonatology and experience in conducting clinical trials who is not otherwise associated with the study. We will halt enrollment during this analysis. If there is > 1 serious adverse events (SAEs) related to the drug in any cohort, the study will be temporarily halted for an *ad hoc* safety review.

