10.1.6 Safety Oversight

Safety oversight will be under the direction of an ISM with expertise in neonatology and clinical trials. The monitor will be independent from the study conduct and free of conflict of interest. The monitor will perform a safety analysis following the treatment period in the final cohort 1 participant and prior to enrollment in cohort 2, or on an *ad hoc* basis if there is > 1 SAE related to the drug in any cohort.

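### The halting rule counts drug-related SAEs without regard to severity, so one drug-related death or life-threatening event brings no automatic pause or referral to the independent safety monitor

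*Combined protocol and SAP*

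**What the plan says.** Two sections carry the rule. Section 9.4.4 states: "If there is > 1 serious adverse events (SAEs) related to the drug in any cohort, the study will be temporarily halted", for an unscheduled safety review. Section 10.1.6 has the independent safety monitor carry out a review between the cohorts, or on an ad hoc "basis if there is > 1 SAE related to the drug in any cohort".

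The SAE definition in 8.3.2 puts death and life-threatening events in one list with "Inpatient hospitalization or prolongation of existing hospitalization" and other categories. Each counts once toward the threshold.

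Section 8.3.3.2 judges relatedness in two ways. The Related category is met if the event is known to occur with the drug, if a causal link is reasonably possible, "or there is a temporal relationship between the study intervention and event". Separately, the investigator asks whether there is a reasonable possibility that the drug caused the event, "where an affirmative answer designates the event as a suspected adverse reaction".

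Under 8.3.6 every SAE goes immediately to the investigator, and the report "must include an assessment of whether there is a reasonable possibility that the study intervention caused the event". FDA must be told of any "unexpected fatal or life-threatening suspected adverse reaction as soon as possible, but in no case later than 7 calendar days". Under 8.3.3.3 an event is "unexpected if the nature, severity, or frequency of the event is not consistent with the risk information previously described". Section 8.4.2 gives 7 days for reporting to the IRB an unanticipated problem that is an SAE. Section 10.1.2 allows suspension for reasonable cause, including unexpected or unacceptable risk.

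**The concern.** Section 2.2 says that the safety of caffeine in neonates with HIE is unknown. In such a trial, a death or life-threatening event that the investigator thinks the drug may have caused is the event for which one would most want a pause and an independent look before the next infant is dosed. The rule reserves both for a second related SAE in the same cohort. Two related prolonged hospitalizations would halt the study, whereas one related death would not.

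After such a death, it is left to discretion whether enrolment pauses and whether the monitor sees the case promptly. The gap matters most in cohort 2, which receives twice the maintenance dose (10 versus 5 mg/kg) and has no scheduled safety review.

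**Working it through.** **1. What follows a single drug-related fatal or life-threatening event**

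| Route | Who acts | Automatic pause? | Monitor named? |
|---|---|---|---|
| 9.4.4 and 10.1.6, ad hoc review | Monitor | Not at one event | Not at one event |
| 8.3.6, SAE report | Investigator, at once | No | No |
| 8.3.6, expedited report | FDA, 7 days, if unexpected | No | No |
| 8.4.2, unanticipated problem | IRB, 7 days, if criteria met | No | No |
| 10.1.2, suspension | Not assigned | No, discretionary | No |
| Synopsis, 9.4.4 and 10.1.6, scheduled review | Monitor | Enrolment halts for the review between cohorts | Yes, between cohorts only |

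Because 8.3.3.3 lets severity alone make an event unexpected, the 7-day FDA report would normally apply. No route combines a single event with an automatic pause or a referral to the monitor. This result needs no arithmetic.

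**2. How often it could happen**

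The plan gives no operating characteristics for the rule and no rate of related SAEs, so there is no figure to reproduce. What follows is illustration on assumed inputs.

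Let r be the per-infant risk of a related fatal or life-threatening event, and s the per-infant risk of at least one other related SAE, taken as independent. In a cohort of 9 (section 4.1), the chance of exactly one such event with the rule never triggered is 9 × r × (1 − r)^8 × (1 − s)^9.

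With s = 0 this is 9 × 0.05 × 0.95^8 = 0.299 and 9 × 0.10 × 0.90^8 = 0.387.

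| s | r = 5% | r = 10% |
|---|---|---|
| 0 (upper bound) | 29.9% | 38.7% |
| 10% | 11.6% | 15.0% |
| 20% | 4.0% | 5.2% |
| 30% | 1.2% | 1.6% |
| 40% | 0.3% | 0.4% |

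**3. Independence raises these figures**

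The rule counts events, and an infant with a life-threatening event is more likely to have a second SAE. Suppose that half of such infants have another related SAE, with s still 10% overall. The chance that an infant has only the index event is then r/2, and the chance of neither kind is 1 − r − 0.10 + r/2. The results are:

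- r = 5%: 9 × 0.025 × 0.875^8 = 7.7%, against 11.6%.
- r = 10%: 9 × 0.05 × 0.85^8 = 12.3%, against 15.0%.

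**4. Infants dosed afterwards**

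If there is one event, no other related SAE, strictly sequential enrolment and nobody uses the suspension power, the event is equally likely in any of the 9 infants. The mean number still to be dosed in that cohort is (8 + 7 + … + 0)/9 = 36/9 = 4, with a range of 0 to 8.

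**5. Extra pauses under a single-event trigger**

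Table 2 gives mortality of 19–33% in cooled infants in earlier trials: 18 × 0.19 = 3.4 and 18 × 0.33 = 5.9 expected deaths. If 10% are judged a reasonable possibility (assumed), that is 0.3 to 0.6 deaths that would pause enrolment. If 25% are, it is 0.9 to 1.5. Non-fatal life-threatening reactions would add to this; events that coincide with the existing trigger would subtract.

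**The case against.** The strongest reply is that this is a choice of threshold, and that the trial is already guarded. It has an independent monitor, a halt and review before escalation, and a numeric rule. A single serious event is reported quickly, and 10.1.2 allows suspension. Section 10.1.6 also places safety oversight generally under the monitor. All of that stands. What remains is narrow: whether a pause and a referral are automatic or discretionary, chiefly in cohort 2.

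A second reply is that the rule fires easily, because timing alone can make an event Related and the SAE list is broad. These are critically ill infants, so s may well be high and the larger figures above hard to credit. This also stands, and it limits the size of the point. It does not remove it: a rule that is sensitive to lesser events still does not guarantee independent review of one death.

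Third, not all the text is available. The manual of procedures, the clinical monitoring plan and section 10.1.5 on key roles and governance could each hold a duty to notify the monitor. The point is therefore limited to the text supplied.

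Three stronger readings are tempting but not supported:

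- A reader might infer that a drug-attributed death could pass unattended. Sections 8.3.6, 8.4.2 and 10.1.2 rule that out.
- A reader might take 30–39% as the likely frequency. It requires that no other related SAE occurs at all.
- A reader might conclude that cohort 2 is unsafe because 20 + 10 + 10 = 40 mg/kg exceeds the 36 mg/kg that 2.2 links to a lower seizure threshold. Section 2.2 does not say whether that figure is single or cumulative, and 4.3 says that the higher maintenance dose is consistent with use in apnea of prematurity. Section 2.2 also calls caffeine safety well described in apnea of prematurity, and Table 2 shows 2 deaths in 16 among caffeine-treated cooled infants. That is small and observational, but no sign of excess mortality.

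**Conclusion.** The point holds as a low-cost improvement to a stated rule; it is not an error and invalidates no analysis. In the text supplied, one drug-related death or life-threatening event triggers neither an automatic pause nor a referral to the monitor. In cohort 1 it would reach the monitor only between cohorts, possibly after the remaining infants were dosed; in cohort 2 no scheduled review is left.

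This conclusion rests on the wording. Its frequency cannot be derived from the documents: the illustrative range of 0.3% to 39% per cohort depends wholly on assumed rates and on independence, which inflates it. If 20% or more of infants have another related SAE, the figure is about 5% or less. The size should not be used to raise the weight of the point.

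**What to change.** In 9.4.4 and 10.1.6, add that any single fatal or life-threatening SAE judged a suspected adverse reaction, by the reasonable-possibility question in 8.3.3.2, pauses new enrolment at once. The existing monitor is notified promptly and completes an ad hoc review before the next infant is dosed. Keep the more-than-one threshold for other related SAEs.

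The rule would then contain two causality tests, so say that this is deliberate: the single-event trigger uses the narrower reasonable-possibility test, so that a death linked by timing alone does not stop enrolment, while the more-than-one trigger keeps the broader Related category. Section 8.3.6 already requires the narrower assessment for every SAE.

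The change needs protocol wording only, with no new committee, staff or assessment. The downside is possibly one or so extra enrolment pauses on the assumptions above. The first dose must be given before 24 hours of age (8.1.2), so some eligible infants born during a pause may pass that window and be lost to the trial.

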9.4.4.1 Clinical Definitions

1. Sepsis- Positive blood culture and ≥ 7 days of antibiotic treatment
2. Disseminated Intravascular Coagulopathy: Transfusion of platelets, fresh frozen plasma, or cryoprecipitate
3. Hypotension: Requiring inotrope or vasopressor support
4. Hypertension: Requiring antihypertensive medication
5. Hepatic dysfunction: AST > 200 IU/L or ALT > 100 IU/L
6. Acute Kidney Injury (AKI), stage 1-3 classified using Kidney Disease: Improving Global Outcomes (KDIGO) system (**Table 5**). We will use the highest serum creatinine per 24-hour period. A participant will be assigned a stage if they meet either serum creatinine or urine output criteria listed below.

Table 5. AKI KDIGO Classification⁶¹

Stage	Serum Creatinine (SCr)	Urine Output
0	No change in SCr or rise <0.3 mg/dL	≥ 1.0 mL/kg/hour
1	SCr rise ≥ 0.3 mg/dL within 48 hours or SCr rise ≥ 1.5 - $1.9 \times$ reference SCr ^a within 7 days	> 0.5 and ≤ 1 mL/kg/hour

2	SCr rise \geq 2.0-2.9 X reference SCr ^a	> 0.3 and \leq 0.5 mL/kg/hour
3	SCr rise \geq 3 X reference SCr ^a or SCr \geq 2.5 mg/dL or receipt of dialysis	\leq 0.3 mL/kg/hour

^aReference SCr will be defined as the lowest previous SCr value

7. **Persistent Pulmonary Hypertension**: Requiring inhaled nitric oxide and fraction of inspired oxygen >0.50
8. **Thrombocytopenia**: Platelet count $< 100,000$ per μL
9. **Seizures** will be defined by the receipt of > 1 AED, as we are interested in identifying seizures which are difficult to control.
10. **Necrotizing Enterocolitis** - Bell Stage II or III⁵⁷

9.4.5 Baseline Descriptive Statistics

Not applicable.

9.4.6 Planned Interim Analyses

Not applicable

9.4.7 Sub-group Analyses

Not applicable

9.4.8 Tabulation of Individual Participant Data

Individual participant data will be listed by measure and time point.

9.4.9 Exploratory Analyses

Epigenetic markers

We will relate the CpG methylation signatures of genes encoding for cytochrome P450 enzymes to caffeine exposure and metabolism.

10 SUPPORTING DOCUMENTATION AND OPERATIONAL CONSIDERATIONS

10.1 Regulatory, Ethical, and Study Oversight Considerations

10.1.1 Informed Consent Process

10.1.1.1 Consent/Accent and Other Informational Documents Provided to Participants

Consent forms describing in detail the study intervention, study procedures, and risks are given to the participant's parent or guardian and written documentation of informed consent is required prior to starting intervention/administering study intervention. The following consent materials are submitted with this protocol: consent form in English.

10.1.1.2 Consent Procedures and Documentation

Informed consent is a process that is initiated prior to the individual's parent or guardian agreeing to participate in the study and continues throughout the individual's study participation. Consent forms will be Institutional Review Board (IRB)-approved and one of the participant's parents or guardians will be asked to read and review the document. The investigator will explain the research study to the parent or guardian and answer any questions that may arise. A verbal explanation will be provided in terms suited to the parent's comprehension of the purposes, procedures, and potential risks of the study and of their rights as research participants. The parent or guardian will have the opportunity to carefully review the written consent form and ask questions prior to signing. The parent or guardian should have the opportunity to discuss the study with their family or surrogates or think about it prior to agreeing to participate. The parent or guardian will sign the informed consent document prior to any procedures being done specifically for the study. Parents/guardians must be informed that participation is voluntary and that they may withdraw their neonate from the study at any time, without prejudice. A copy of the informed consent document will be given to the parent or guardian for their records. The informed consent process will be conducted and documented in the source document (including the date), and the form signed, before the participant undergoes any study-specific procedures. The rights and welfare of the participants will be protected by emphasizing to the parent or guardian that the quality of their medical care will not be adversely affected if they decline to participate in this study.

10.1.2 Study Discontinuation and Closure

This study may be temporarily suspended or prematurely terminated if there is sufficient reasonable cause. Written notification, documenting the reason for study suspension or termination, will be provided by the suspending or terminating party to study participants, investigator, funding agency, the Investigational New Drug (IND) or Investigational Device Exemption (IDE) sponsor and regulatory authorities. If the study is prematurely terminated or suspended, the Principal Investigator (PI) will promptly inform study participants, the Institutional Review Board (IRB), and sponsor and will provide the reason(s) for the termination or suspension. Study participants will be contacted, as applicable, and be informed of changes to study visit schedule.

Circumstances that may warrant termination or suspension include, but are not limited to:

- Determination of unexpected, significant, or unacceptable risk to participants
- Demonstration of efficacy that would warrant stopping
- Insufficient compliance to protocol requirements
- Data that are not sufficiently complete and/or evaluable
- Determination that the primary endpoint has been met
- Determination of futility

Study may resume once concerns about safety, protocol compliance, and data quality are addressed, and satisfy the sponsor, IRB and/or Food and Drug Administration (FDA).

10.1.3 Confidentiality and Privacy

Participant confidentiality and privacy is strictly held in trust by the participating investigators, their staff, and the sponsor(s) and their interventions. This confidentiality is extended to cover testing of biological samples and genetic tests in addition to the clinical information relating to participants. Therefore, the study protocol, documentation, data, and all other information generated will be held in strict confidence. No information concerning the study or the data will be released to any unauthorized third party without prior written approval of the sponsor.

All research activities will be conducted in as private a setting as possible.

The study monitor, other authorized representatives of the sponsor, representatives of the Institutional Review Board (IRB), regulatory agencies or pharmaceutical company supplying study product may inspect all documents and records required to be maintained by the investigator, including but not limited to, medical records (office, clinic, or hospital) and pharmacy records for the participants in this study. The clinical study site will permit access to such records.

The study participant's contact information will be securely stored at each clinical site for internal use during the study. At the end of the study, all records will continue to be kept in a secure location for as long a period as dictated by the reviewing IRB, Institutional policies, or sponsor requirements.

10.1.4 Future Use of Stored Specimens and Data

Data collected for this study will be analyzed and stored at the University of North Carolina at Chapel Hill. During the conduct of the study, an individual participant can choose to withdraw consent to have biological specimens stored for future research. However, withdrawal of consent with regard to biosample storage may not be possible after the study is completed.

10.1.6 Safety Oversight

Safety oversight will be under the direction of an ISM with expertise in neonatology and clinical trials. The monitor will be independent from the study conduct and free of conflict of interest. The monitor will perform a safety analysis following the treatment period in the final cohort 1 participant and prior to enrollment in cohort 2, or on an *ad hoc* basis if there is > 1 SAE related to the drug in any cohort.

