Description of Study Intervention:	
Cohort 1 (N = 9): Caffeine IV 20 mg/kg loading dose, followed by 5 mg/kg q 24 hours x 2 doses.
 
Cohort 2 (N = 9): Caffeine IV 20 mg/kg loading dose, followed by 10 mg/kg q 24 hours x 2 doses.
 
Note: An interim safety analysis will be conducted following the follow-up period in the final cohort 1 participant and prior to enrolling in cohort 2.

Study Duration:	24 months
Participant Duration:	24 months

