1.2 Schema

1.3 Schedule of Activities (SoA)

	Screen/ Baseline	Treatment	Follow-up Period	Discharge/Transfer /Death	Final study assessment
Time point	< 24 hours postnatal age	Study day 1-3	7 days following last caffeine dose		18-24 Months
Informed consent	X				
Demographics	X				
Neurological Exam	X			X	X
Weight	X	X	X	X	X
Medical history	X				X ¹
Respiratory Support	X ²	X ²	X ²	X	
Laboratory evaluations ³	X	X	X		
Urine output	X	X	X		
Caffeine administration ⁴		X			
Concomitant medications		X	X		
Adverse events ⁵		X	X		
PK sampling ⁶		X	X		
Epigenetic sampling ⁷		X	X		
Clinical events of interest ⁸		X	X		
Head imaging ⁹		X	X	X	
Hearing screen				X	
Surgical procedures		X	X	X	
Bayley-III composite scores and GMFCS					X

¹ Follow-up visit will include information on hearing impairment requiring hearing aids, blindness, and cerebral palsy diagnosis. ² Highest respiratory support (room air, oxyhood, nasal cannula/CPAP, or mechanical ventilation) and maximum FIO₂ exposure during each 24-hour period. ³ See Section 8.2.1. ⁴ Includes exact start, stop, and flush times for all caffeine doses. ⁵ Seizures requiring > 1 anti-epileptic drug and necrotizing enterocolitis are adverse events of special interest. ⁶ Date and time for each sample. ⁷ Obtained from scavenged blood samples, if available. ⁸ Includes death, sepsis, disseminated intravascular coagulopathy, hypotension, hypertension, hepatic dysfunction, acute kidney injury, persistent pulmonary hypertension, and thrombocytopenia. ⁹ Includes cranial ultrasounds and head CT, if done per standard of care, and brain MRI.

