2.3.3 Assessment of Potential Risks and Benefits

Given the high incidence of mortality and NDI in neonates with HIE, we propose that the value of the information to be gained in this study outweigh the potential risks of exposure to caffeine. We have minimized these potential risks by using a dose of caffeine that is equivalent to the dose ranges used on-label for apnea of prematurity in preterm neonates. We will exclude neonates with difficult to control seizures (i.e., receiving > 1 anti-epileptic drug [AED]), tachycardia (defined as heart rate > 180 beats per minute for > 4 hour), or major congenital anomalies, including congenital heart disease. We will collect data on seizures and necrotizing enterocolitis as safety events of interest. We will review safety data prior to dose escalation between cohorts.

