4 STUDY DESIGN

4.1 Overall Design

This is a phase I, open-label, dose-escalating PK and safety study of caffeine in neonates with HIE undergoing therapeutic hypothermia. There will be two cohorts, with two caffeine dosing regimens (see **Section 6.1.2, Dosing and Administration**). Each cohort will consist of 9 neonates and the intervention duration will be 48 hours. An interim safety analysis will be conducted following the follow-up period in the final cohort 1 participant (see **Section 9.4.4, Safety Analyses**) to assess for safety prior to enrollment in cohort 2. We hypothesize that drug clearance will be $\geq 20\%$ lower than expected for gestational age and birth weight and that the incidence of adverse events will be similar to those in published trials of therapeutic hypothermia.

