8.1.3 Follow-up Period

The following assessments will be recorded in the CRF for the follow-up period (7 days following the final dose of caffeine):

1. Daily weight (grams)
2. Highest respiratory support (room air, oxyhood, nasal cannula/CPAP, or mechanical ventilation) and maximum FIO₂ exposure during each 24-hour period
3. Concomitant medications (see Section 6.5)
4. Laboratory evaluations (see Section 8.2.1)
5. Urine output (in mL/kg/hour)
6. PK sampling (date and time) (see Section 8.2.2)
7. Epigenetic sampling (date and time) (see Section 8.2.2)
8. Clinical events of interest: sepsis, disseminated intravascular coagulopathy, hypotension, hypertension, hepatic dysfunction, acute kidney injury, persistent pulmonary hypertension, and thrombocytopenia.
9. Adverse events (see Section 8.3), including seizures requiring > 1 AED and NEC
10. Head imaging results (including cranial ultrasounds and head CT, if obtained per standard of care, and brain MRI) (see Section 8.1.6)

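### Section 10.1.6 times the pre-cohort-2 safety review from the end of treatment; sections 1.1, 4.1 and 9.4.4 time it from the end of the 7-day follow-up

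*Combined protocol and SAP*

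**What the plan says.** **Timing of the review.** Four places in the combined protocol and SAP set the start of the safety review that separates the two dose cohorts.

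- Section 10.1.6, Safety Oversight: "The monitor will perform a safety analysis following the treatment period in the final cohort 1 participant and prior to enrollment in cohort 2".
- Section 9.4.4, Safety Analyses: "Following the follow-up period in the final cohort 1 participant, there will be an interim safety analysis performed by an independent safety monitor".
- Section 1.1, Synopsis: "An interim safety analysis will be conducted following the follow-up period in the final cohort 1 participant and prior to enrolling in cohort 2".
- Section 4.1, Overall Design: "An interim safety analysis will be conducted following the follow-up period in the final cohort 1 participant".

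Treatment and follow-up are separate periods. They have separate columns in section 1.3 and separate sections, 8.1.2 and 8.1.3. Treatment is study days 1 to 3. Follow-up is "7 days following last caffeine dose" in section 1.3 and "7 days following the final dose of caffeine" in section 8.1.3.

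**Role of the review.** Section 2.3.3 lists it among the measures that limit risk: "We will review safety data prior to dose escalation between cohorts". Section 9.4.4 adds: "We will halt enrollment during this analysis".

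**Adverse event window.** Section 3, section 8.2 and the last sentence of 8.3.4 carry the review or recording of adverse events to discharge from the initial hospitalization. The adverse event row in 1.3 is marked only under treatment and follow-up. The discharge list in 8.1.4 has no adverse event item, and the first sentence of 8.3.4 refers only to the 7-day follow-up.

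**The concern.** The review decides whether the maintenance dose goes from 5 to 10 mg/kg, so the data it covers should be fixed without ambiguity. Section 10.1.6 is headed Safety Oversight and is where a monitor would naturally look for the timing of the task. It gives an earlier trigger than the other three sections. Someone working from it could convene the review once the last cohort 1 infant had finished dosing, and the monitor could clear escalation before seeing that infant's follow-up.

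The adverse event point is smaller. Staff who work from the schedule or the discharge list, rather than from 8.3.4, have no prompt to look for events between the end of follow-up and discharge.

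**Working it through.** The plan gives no statistical figure to reproduce here. The check is a comparison of text and a short timeline.

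**Is it one review?** Sections 9.4.4 and 10.1.6 both assign it to the independent safety monitor. Sections 1.1, 4.1 and 10.1.6 all place it before cohort 2 enrollment, and 4.1 refers the reader to 9.4.4. All four tie it to the final cohort 1 participant. It is one review with two stated triggers.

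| Section | Trigger in the final cohort 1 participant |
|---|---|
| 1.1 | end of follow-up |
| 4.1 | end of follow-up |
| 9.4.4 | end of follow-up |
| 10.1.6 | end of treatment |

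**How far apart are the triggers?** Time is counted from that infant's loading dose.

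- Doses are 24 hours apart and there are two maintenance doses (6.1.2, 8.1.2), so the last dose is at 2 × 24 = 48 h.
- Treatment ends between the last dose (48 h) and, at the latest, the end of study day 3 (3 × 24 = 72 h).
- Follow-up ends 7 days after the last dose: 48 + 7 × 24 = 48 + 168 = 216 h, or 9 days.
- Difference: 216 − 48 = 168 h (7 days) down to 216 − 72 = 144 h (6 days).

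**How much data is at issue?** Cohort 1 has 9 infants. If the other 8 have completed follow-up, a review at the earlier trigger lacks up to 7 days for 1 of 9. If another infant finished dosing in the same week, part of its follow-up would also be missing. The documents give no accrual rate, so I put no figure on that.

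**Can one date satisfy every section?** Yes. A review at 216 h or later is after both treatment and follow-up. A review at 48 to 72 h satisfies 10.1.6 only.

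**Adverse event window.**

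| Place | Runs to |
|---|---|
| Section 3 | discharge |
| 8.2 | end of the initial hospitalization |
| 8.3.4, last sentence | discharge |
| 8.3.4, first sentence | mentions 7-day follow-up only |
| 1.3, adverse event row | follow-up column |
| 8.1.4 | no adverse event item |

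The 8.1.4 list agrees with the table row, so the missing mark in 1.3 is unlikely to be a fault of text extraction.

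**The case against.** The strongest reply is that all sections bind together. A review at the end of dosing would breach 1.1, 4.1 and 9.4.4, whereas a review after follow-up breaches nothing. On that view 10.1.6 is a wording slip that resolves itself. This largely stands: the intent is not in doubt, and the early review is open only to someone who follows 10.1.6 without the other three. What remains is that the text governing a dose-escalation decision should not depend on being checked against three other places.

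A reader might infer more than the documents support, in three ways.

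- *That the last infant's week goes unobserved.* It does not. Section 8.1.3 records adverse events, the events of special interest, laboratory values and clinical events throughout those 7 days. At most, the monitor's review would lack them.
- *That a serious event in that week would never reach the monitor.* The SAE and unanticipated-problem routes in 8.3.6 and 8.4.2 do not name the monitor. But 10.1.6 puts safety oversight generally under the monitor, and the text available for review is not complete. The ad hoc trigger of more than one drug-related SAE is a separate design choice, and correcting the review date would not alter it.
- *That adverse events after follow-up are not collected.* They are required. The last sentence of 8.3.4 runs to discharge, and 8.3.5 places reportable events on the electronic case report form. The first sentence of 8.3.4 says when events may come to notice and sets no end date. Days without a mark in the schedule are not days outside the recording duty, so no share of events or of hospital stay can be called missed.

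**Conclusion.** The inconsistency is real and lies in current operative text. Section 10.1.6 alone would let the escalation review take place about 6 to 7 days earlier than 1.1, 4.1 and 9.4.4 require. The cost would be up to 7 days of follow-up data for one of nine infants. That size assumes the other eight have finished follow-up and that the review is held as soon as 10.1.6 allows. The documents do not support the conclusion that the trial plans to escalate without follow-up data, because three sections say the opposite. The correction should be made because this is a safety decision point and the remedy is trivial. The adverse event point is one of alignment only: the duty to record to discharge already exists, and the schedule and discharge list should reflect it.

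**What to change.** 1. In 10.1.6, change 'treatment period' to 'follow-up period', so that all four sections give one trigger.
2. Add one chart-review item for adverse events, including the events of special interest (necrotizing enterocolitis and seizures needing more than one anti-epileptic drug), to the Discharge/Transfer/Death column of 1.3 and to the 8.1.4 list.
3. Reword the first sentence of 8.3.4 to run to discharge, as its last sentence does.

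The cost is one phrase, one sentence and one chart-review item. There are no new visits, blood draws or participants, and sample size, power and estimates are unchanged. The review would fall at most 7 days later than 10.1.6 taken alone, at the time the other three sections already set.
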